A power analysis was also considered for shoulder function, a secondary clinical outcome. It demonstrated that at least thirty-four cases must complete the study (seventeen cases in each arm- augmented and control) in order to assess the difference between each group. This sample size was statistically derived by an ASES score power analysis, using a power of 0.8, an effect size d of 0.9, an alpha error probability of 0.05, and an allocation ratio of 1. This is assuming an ASES score of 84 at 12 months postsurgical repair in the augmented group (standard deviation of 16) and 72 (standard deviation of 12) for the control group. The ASES data used was derived from a recently completed ArthroFlex rotator cuff repair study for which data is on file at LifeNet Health. Again, with the assumption that the control group will have a failure rate of approximately 40% and the augmented group will have a failure rate of approximately 20%, at least 30 should be randomized in the control group and 22 in the augmented group to assess a difference in shoulder function.

Once data is acquired for 15 subjects in each group, a post-hoc power analysis will be conducted to confirm that alpha and beta error probabilities are still under the accepted limits.

The primary analysis will be conducted on both the intent to treat and the per protocol populations. The intent to treat population will be comprised of all subjects that have completed rotator cuff repair surgery. The per protocol population will be comprised of all subjects that have completed all study visits and did not have any major protocol violations (e.g., missed visits, noncompliance with postsurgical instructions, etc.). Standard adjustments to analyses for pre-specified or baseline-suggested clinical covariates will be made; these covariate-adjusted analyses will be considered secondary analyses. Primary analysis results will be declared statistically significant if the two-sided p-value is less than 0.05.

Safety analyses will be performed on the intent to treat population and will include the incidence of treatment-emergent AEs and clinically significant changes in vital signs and

physical examinations. Impact of treatment on infection rate, treatment emergent AEs, and changes in vital signs and physical examination will all be assessed.

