Safety data will be summarized with descriptive statistics by treatment group and also by visit, where applicable. AE data will be listed individually and summarized by system organ class and preferred terms within a system organ class for each treatment group.

All statistical comparisons will be made using the Statistical Package for Social Science (SPSS) version 16.0 software. Results will be reported as an aggregate.

Statistical analysis will be performed by the orthopaedic research fellows in conjunction with Cleveland Clinic-Main biostatistician.

6. Study Product Description

ArthroFlex (A-FLEX) is not considered investigational and is currently available. The material is classified as a human and cellular tissue product under Food and Drug Administration (FDA) regulations and thus is not subject to any clinical evaluations before use. LifeNet Health uses several steps to ensure that allograft tissue is safe for use with patients. Extensive donor screening is performed to prevent risk of disease transmissions. There is a medical and social history taken from every donor, and questionable donors are refused. Blood is drawn from each donor for testing to rule out diseases such as HIV, hepatitis, and syphilis. Each section of recovered tissue is tested for any bacteria. In addition, tissue used to make A-FLEX is treated with antibiotic to inactivate bacteria. The tissue is also cleaned thoroughly with detergent, enzymes, and solvent to remove cells from tissue. This MATRACELL™ technology also effectively removes donor DNA from the ADM ensuring a biocompatible scaffold to facilitate repair. All these screenings, tests, and treatments are designed to eliminate the risk of disease transmission. The remaining intact acellular framework contains native growth factors, proteoglycans, hyaluronic acid, collagen, fibronectin, and elastin, therefore promoting wound healing.

A-FLEX is terminally sterilized with low dose gamma irradiation to provide a medical-device grade Sterility Assurance Level (SAL) of 10^{-6} .

Labeling

Since this will be an open-label study, study product will be identified. The Instructions for Use for A-FLEX will be provided in the site study binders.

Storage and Handling of Investigational Product

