A-FLEX is provided in a sealed and sterile pouch and is stored at room temperature (between 15°C and 30°C). A-FLEX should not be frozen or refrigerated. It should be stored in its original cardboard sleeve. There should be minimal excessive exposure to light and A-FLEX should be protected from excessive heat. The product should not be used past the expiration date indicated

on the label. A-FLEX should not be used if it is damaged, if the packaging integrity is compromised, if the color of the product is other than white, or if the temperature dot on the package is not present. Rinsing is not required prior to application; however, it may improve handling.

Accountability Procedures for the Study Products

Investigation product records must include the following:

- Receipt, date and quantity, and batch or lot number
- Disposition dates and quantity administered to each subject
- Inventory records
- All correspondence related to the study product

All product records should be stored in the study binder with product instructions for use.

7. Confidentiality of Data

The only patient identifying information to be used will be the medical record number in order to facilitate collection and organization of data and ensure that serial US and shoulder surveys are attributed to the same patient. All data will be recorded in a password-protected REDCap database. The principal investigator, orthopaedic research fellows, research coordinators, and the study's preceptors will be the only individuals allowed access to this information.

8. Adverse Events and Data Monitoring Committee

All adverse events (AE) will be recorded. Details to be documented include the nature, onset, duration, severity, relationship to the device, relationship to the operative procedure and outcome of each event.

Most likely adverse events:

- Infection
- Injury to nerves and blood vessels
- Chronic pain or Complex regional pain syndrome

Note: The above-mentioned AE are not related to the use of ECM scaffold graft. They are potential complications associated with rotator cuff repair.

Potential serious adverse events related to ECM scaffold graft use:

- Anaphylactoid or anaphylactic reaction to ECM allograft.

If an unanticipated (in nature, severity or frequency) or serious (fatal, life-threatening or permanently disabling) adverse event arises, the study will be halted and the IRB

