notified. The situation will be discussed among surgical faculty, and if there is a prudent solution, it will be presented to the IRB for approval. If there are no effective solutions, the investigators will have no choice but to discontinue the study.

Data will be reviewed by the PI and physicians conducting the study. The ECM scaffold grafts have not been linked to potentially serious or life-threatening complications. Our research will limit the potential for complications even further by screening and excluding patients with a known allergy to materials of porcine origin. Lastly, the ECM grafts are FDA-approved scaffold material that is indicated for reinforcement or augmentation of soft tissue repairs. In view of this, we will not be deviating from the standard of care by using the ECM allograft and the investigators do not anticipate having to discontinue the study or having to alter the protocol based on interim results. For these reasons, an independent data monitoring committee will not be needed or used.

9. Consent

In a private, outpatient setting, the PI or one of the research coordinators involved in the study will describe in detail the characteristics of the research study. Understandable language will be used. The process of pre-operative assessment, randomization, treatment, data collection and analysis along with the potential risks/benefits of the study are to be described in detail. Furthermore, the methods of maintaining data security and confidentiality will be outlined. The patient is to be explicitly told that he or she does not have to participate in the study and that regardless of his/her decision, will receive the best care this hospital can provide.

The informed consent process will take place during the patient's pre-operative clinical visit. The original consent form will be kept with study records by the principal investigator in a secure location, and a copy of the consent will be given to the subject. The subject's decision to participate will be documented in his or hers electronic record. A copy of the consent may be placed in the hospital record.

10. Principal Investigators

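### Section 8 asks for device relationship to be documented for each adverse event, but its Note answers that question in advance for the most likely events (minor)

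*Combined protocol and SAP*

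**What the plan says.** Section 8 (Adverse Events and Data Monitoring Committee) opens with full capture: "All adverse events (AE) will be recorded". It then sets out what is recorded: "Details to be documented include the nature, onset, duration, severity, relationship to the device, relationship to the operative procedure and outcome of each event". Device and procedure are thus two separate judgements, made for every event.

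The section next lists three most likely events: infection, nerve or vessel injury, and chronic pain or complex regional pain syndrome. Two sentences follow the list. The first is "Note: The above-mentioned AE are not related to the use of ECM scaffold graft". The second is "They are potential complications associated with rotator cuff repair". A separate list of potential serious events related to the graft has one entry, an anaphylactoid or anaphylactic reaction.

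Later in Section 8, in the argument for having no independent monitoring committee, the plan says: "The ECM scaffold grafts have not been linked to potentially serious or life-threatening complications". Data are to be reviewed by the principal investigator and the physicians conducting the study.

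Section 5 (Sample Size Justification and Statistical Analysis) covers the safety analysis: "Impact of treatment on infection rate, treatment emergent AEs, and changes in vital signs and physical examination will all be assessed". Adverse events are listed one by one and tabulated for each arm by organ class and preferred term. Section 6 states that the study is open-label.

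**The concern.** A causality field is useful only if its answer is open when the event occurs. Here the plan asks the assessor to judge whether the device was involved, and a few lines later tells the same assessor that for the commonest events it was not. The statement has no qualifier such as 'usually' or 'in most cases'. The graft-related list that follows makes the split look complete: expected events on one side, anaphylaxis on the other.

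What is at stake is the attribution recorded for an infection or a chronic pain syndrome in a grafted shoulder. The assessor may know the arm, and the documents name no independent reviewer of the coding.

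**Working it through.** The plan gives no figure for relatedness or for an expected infection rate, so there is nothing to reproduce. The check is a comparison of the texts.

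1. **Field against Note, within Section 8.** The field covers "relationship to the device, relationship to the operative procedure and outcome of each event". It makes no exception for the listed events. The Note gives one fixed answer for the first of these items, for three event types. Both cannot govern the same entry: either the relationship is judged for each event, or it is settled beforehand.

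2. **What a literal reading would change.** In the individual listing, the device-relationship entry for infection, nerve or vessel injury and chronic pain would be 'not related' whatever the facts of the case. The nature, onset, duration, severity and outcome of the event would be recorded as before.

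3. **What it would not change.** The Section 5 analysis of treatment on infection rate counts infections by arm, and the organ-class tables count events by arm. Neither is described as restricted to related events, so a miscoded relationship entry leaves every count the same. No summary by relatedness is planned.

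4. **Why the listing still matters.** Comparison by arm is weak for rare events. As context only, assume all 35 patients per arm (Section 1) are in the safety population and borrow the two-sided 0.05 level that Section 5 sets for the primary analysis. With no infections among 35 controls and k among 35 grafted patients, the two-sided Fisher p-value is 2 × C(35,k)/C(70,k):
   - k = 5: 2 × 324,632/12,103,014 = 0.054
   - k = 6: 2 × 1,623,160/131,115,985 = 0.025

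   Six infections against none would be needed to pass 0.05. The Note does not cause this low power. It does mean that a reader facing one or two infections would look to the case-level judgement, which is the entry that the Note settles in advance.

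5. **The two statements about serious risk in Section 8.** One names a potential serious event related to the graft. The other says that grafts have not been linked to potentially serious complications, and uses this as one of several reasons for having no independent committee. A potential event and the absence of a reported link can both be true, but the text does not say so, and the second statement reads more broadly than the first allows.

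**The case against.** The strongest reply is that the Note is not a coding instruction. Its second sentence calls the events complications of the operation, so the pair can be read as describing background surgical risk. Nothing tells assessors how to complete the relationship field, and nothing waives it. This stands: the conflict bites only if the Note is taken at its word.

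A reader might infer that graft-related infections will be zero by rule, and that the trial would then report a falsely reassuring zero out of 35. The documents do not support this. There is no such rule, and the plan calls for no table of graft-related events, so a confidence bound on that zero would measure nothing in the plan.

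A reader might also infer that the Note hides a graft effect on infection, or contradicts Section 5. It does not, because the randomized comparison ignores attribution.

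Nor does Section 6 contradict the Note. It says "Each section of recovered tissue is tested for any bacteria", but it also describes antibiotic treatment and terminal sterilization, which help explain the sponsor's view. The longer incision in the mini-open technique adds little: augmentation may also be arthroscopic, control repairs may be open, and an incision effect is arguably a procedural one.

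Finally, Section 8 has a route to the ethics board for serious or unanticipated events that does not depend on attribution. That is a real safeguard. It is not a full answer, because an infection is already listed as likely. It would reach that route only if it met the section's definition of serious or was unanticipated in severity or frequency.

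**Conclusion.** The internal contradiction holds, and it is minor. The Note prejudges the device-relationship entry for the three most likely event types, in conflict with the requirement in the same section to document that relationship for each event. Its possible effect is confined to the attribution entries in the individual listings. Counts by arm, the infection comparison and the efficacy endpoints are unaffected.

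The conclusion assumes that at least some assessors would take the Note literally. If all read it as background risk, the entries would be unbiased and only the wording would be at fault. The open-label design and the lack of independent review make a literal reading less likely to be noticed, but the documents do not show that it has happened. The tension between the two statements on serious graft risk is a secondary drafting point.

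**What to change.** In Section 8:

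- Replace the Note with wording that the listed events are expected complications of rotator cuff repair and may occur with or without the graft.
- State that relationship to the device is still judged event by event, including for the listed events.
- Reconcile the statement that grafts have not been linked to serious complications with the serious graft-related event listed earlier in the section, for example by separating what has been reported from what is considered possible.

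No change to the Section 5 summaries is needed. The cost is a few sentences in the next amendment, with no new data, visits or patients. Relationship entries already made for these event types should be checked to see whether they followed the Note. The downside is that some events may be coded as possibly graft-related.

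### An anticipated complication that leads to re-operation, graft removal or readmission reaches the IRB only on the study physicians' own judgement, and the plan has no count of such events

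*Combined protocol and SAP*

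**What the plan says.** Section 8 (Adverse Events and Data Monitoring Committee) sets a single trigger. It opens "If an unanticipated (in nature, severity or frequency) or serious" and continues "serious (fatal, life-threatening or permanently disabling) adverse event arises, the study will be halted and the IRB" is notified. Halting and notification are one step; no separate notification route is described.

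The same section commits to full recording: "All adverse events (AE) will be recorded", with details that include "relationship to the device, relationship to the operative procedure and outcome of each event". It names infection, nerve or vessel injury, and chronic or complex regional pain as the likeliest events, and adds a note: "The above-mentioned AE are not related to the use of ECM scaffold graft".

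Under the heading "Potential serious adverse events related to ECM scaffold graft use" it lists anaphylactoid or anaphylactic reaction. Further on it states: "The ECM scaffold grafts have not been linked to potentially serious or life-threatening complications". That statement is one of several reasons given for concluding that "an independent data monitoring committee will not be needed or used". Data review is left to the principal investigator and the physicians running the study, and Section 6 (Labeling) says the study is open-label.

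Section 5 plans individual listings of adverse events, summaries by treatment group, and an assessment of treatment effect on infection rate. It also expects that some patients randomised to control will need augmentation, and says that those withdrawn for this reason may be followed for safety.

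**The concern.** In a surgical trial of an added implant, a complication serious enough to bring the patient back to theatre or to hospital is one that an outside body would normally want to hear about. Here such a complication can fall between the two limbs of the trigger: listed, so anticipated in nature, yet not grave enough for the protocol's meaning of serious. Whether it is reported then depends on an undefined judgement by people who know the allocation and work under a note that already labels the listed events as unrelated to the graft.

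Two things are at stake. The first is timely outside sight of such events in a trial with no independent monitor. The second is a clear comparison at the end, because an infection that resolved on its own and one that led to graft removal would carry the same term in the summary tables.

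**Working it through.** The point turns on wording, and the plan states no figure to reproduce. The check applies Section 8's trigger to five kinds of event and then looks at capture and analysis.

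**Which events reach the IRB**

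- A graft harm that Section 8 does not list: unanticipated in nature, so notified.
- A life-threatening anaphylactic reaction: serious as defined, so notified.
- A milder anaphylactoid reaction: listed, and not life-threatening, so it depends on judgement.
- A nerve injury or pain syndrome that disables permanently: serious as defined, so notified.
- An infection that leads to re-operation, graft removal or readmission, with recovery: listed, so anticipated in nature; not serious as defined. It is notified only if its severity or frequency is judged unanticipated.

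For that last limb Section 8 gives no expected rate, no grade and no number of events. The judgement falls to the open-label study physicians. The documents mention no other event-notification route; whether the IRB's own policy adds one cannot be told from them.

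**What is captured**

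Recording covers every adverse event and its outcome, so an attentive recorder could note a re-operation there. But neither the operative list (Section 3B), the postoperative list (Section 3C) nor the Schedule of Activities names re-operation or readmission. Section 5's summary by organ class and preferred term would count an infection without showing what it led to.

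**By which group it is analysed**

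Section 5 summarises safety by treatment group without saying whether this means assigned or received. Since it also expects control patients to be augmented, the two can differ. A graft-exposed patient could be counted under control, or be lost to safety follow-up, which is optional for those withdrawn.

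**Why revision for re-tear needs separate handling**

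Re-tear is the efficacy failure. With 35 patients per arm and Section 5's planning rates:

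- control: 35 × 0.40 = 14
- augmented: 35 × 0.20 = 7
- total: 14 + 7 = 21 re-tears among 70 patients

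The documents do not say how many would be revised. A rule that notified every re-operation could therefore draw on a pool of about 21 efficacy failures and obscure the complications it is meant to show.

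**The two statements on graft reactions**

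One part of Section 8 lists a potential serious graft-related reaction; another says the grafts have no link even to potentially serious complications. They are in tension, and the second is used in the reasoning against a committee.

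**The case against.** The strongest reply is that the protocol already covers most of this ground. Every adverse event is recorded with its relationship to device and procedure and its outcome, then listed and summarised by treatment group, with infection rate examined as a possible treatment effect. The trigger's first limb covers unanticipated severity and frequency, so it can in principle catch an accumulation in one arm. This stands, and it limits the point to an undefined threshold and a missing line.

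A reader might go further and infer that the likeliest graft harms may never reach the IRB. The documents do not support that. They do not rank graft harms; the likeliest events they list are attributed to the repair. Unlisted harms are unanticipated in nature and go to the IRB.

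A reader might also infer that the final report would hold no count of these complications. That is wrong too: the infection itself would be counted by treatment group. Only the re-operation or readmission has no planned count.

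Finally, the decision against a committee does not rest on one sentence. Section 8 also cites the exclusion for porcine sensitivity, the product's regulatory status and indication, consistency with standard care, and no expected change from interim results. The tension weakens one support and blocks no notification.

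**Conclusion.** The concern holds in a narrow form. An anticipated complication that leads to unplanned re-operation, graft removal or readmission, but does not cause death, threaten life or disable permanently, reaches the IRB only on an undefined judgement by unblinded study physicians, with no independent monitor behind them. No count of re-operations or readmissions is planned, and a summary by assigned arm alone could misplace events in control patients who receive the graft.

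No numerical size is attached. The documents give no re-operation or readmission rate, and the chance of seeing at least one event at some assumed rate would measure neither the reporting gap nor an imbalance between arms. The conclusion assumes that Section 8 is the complete statement of event reporting. It is a cheap improvement to safety oversight; it does not affect the validity of the primary comparison.

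**What to change.** Leave the halt rule unchanged. Notification is tied to halting, so widening the meaning of serious would also widen the halt; a separate line avoids that.

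1. Add to Section 8 that any unplanned re-operation, graft removal or readmission involving the study shoulder, when it is for a complication, is recorded and notified to the IRB.
2. Add to Section 5 a table of these events by graft actually received as well as by assigned arm. Count revisions for re-tear in a separate row; these are tabulated but not notified.
3. Reconcile Section 8's list of potential serious graft reactions with its later statement that the grafts have no such link, and restate the reasons for having no independent committee so that they agree with the reconciled text.

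The cost is a short paragraph in Section 8, one item on the adverse-event form and one table. The downside is a few more IRB notifications; restricting them to complications keeps efficacy failures out of that stream.
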